#### ***Testing the association of candidate SNP genotype and “immune-related colitis”***

We will test the association of each variant and the risk of immune-related colitis by logistic regression adjusting for potential clinical confounders including age and sex. The Benjamini and Hochberg’s (BH) method will be used to control the false-discovery rate (FDR) at 5%.

\* \* \*

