3. In addition, the CA184-022 trial suggested that the frequency of grade 3-4 irAEs was different between the 3 mg/kg and 10 mg/kg ipilimumab doses.
4. Given that the frequency of adverse events for 10 mg/kg may be greater than 3 mg/kg (in the metastatic setting) as tested in CA184-022, the 10 mg/kg dose level may not be the optimal dose for adjuvant treatment of melanoma and the 3 mg/kg should therefore be evaluated.
5. The magnitude of survival benefit for ipilimumab 10 mg/kg given with dacarbazine in untreated melanoma (CA 184-020, Section [1.5.5](#)) was similar to the magnitude of survival benefit for ipilimumab 3 mg/kg given with vaccine in pretreated melanoma by cross-study comparison (CA184-024: HR 0.72 (p = 0.0009), median OS 11.2 vs. 9.1 months; CA 184-020: HR 0.68 (p < 0.0001), median OS 6.4 vs. 10.0 months).
6. At this stage in its conduct, intergroup E1609 trial provides the best opportunity to evaluate the 3 mg/kg ipilimumab dose while evaluating the 10 mg/kg dose.

In summary, 10 mg/kg ipilimumab was originally chosen to be tested as adjuvant melanoma therapy based on the dose ranging studies supporting the highest likelihood of benefit and also acceptable safety profile in the metastatic melanoma setting. Given that the 3 mg/kg dose of ipilimumab is now commercially available as standard therapy for metastatic melanoma after demonstrating efficacy, adjuvant ipilimumab treatment of melanoma requires further evaluation to determine the optimal dose. E1609 would include study endpoints designed to capture relevant safety and efficacy data and adverse event monitoring for severity, duration, requirement for and duration of corticosteroid and other immunosuppressant use.

---

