#### **XIX.1 Hypotheses**

1. Based on significant preliminary data generated by our group and others we hypothesize that a baseline and /or early-on treatment prognostic biomarker signature in relation to ipilimumab and IFN $\alpha$  can be generated by assessing specific markers of the pro-inflammatory immune response and of immunosuppression in both tumor tissue and in circulating blood, when evaluated simultaneously due to the common systems biology.
  2. The prognostic biomarker signature generated will have therapeutic predictive value in relation to ipilimumab.
  3. Based on significant preliminary data we hypothesize that clustered genomic variants specific to patients who develop immune-related colitis after ipilimumab predict this toxicity.
- 

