### 3. Prediction of Autoimmune Colitis

---

**Clustered genomic variants specific to patients who develop immune-related colitis after ipilimumab may predict this toxicity (Tarhini et al, submitted to ASCO 2014)**

Data generated in the context of UPCI 08-144 trial of neoadjuvant ipilimumab and funded by NIH award P50CA121973. These data have been submitted for presentation at the 2014 ASCO Annual Meeting (*Tarhini et al., Clustered genomic variants specific to patients who develop immune-related colitis after ipilimumab may predict this toxicity*). We identified a genomic signature to predict colitis predisposition among patients undergoing neoadjuvant ipilimumab therapy for locally/regionally advanced operable melanoma.

Rev. 3/15 **XIX.5 Tissue/Specimen Type**

1. Tumor tissue: Paraffin Block or Unstained Slides
2. Body fluids: Serum, Lymphocytes
3. Derivatives: DNA (genomic)

The project plans to test specimens from up to 1600 subjects depending on the availability of biospecimens. The tumor tissue blocks/slides are banked at the ECOG-ACRIN Central Biorepository and Pathology Facility. The research blood/blood products are banked at the ECOG-ACRIN Immune Monitoring and Cellular Products Laboratory (IMCPL) at the University of Pittsburgh Cancer Institute (UPCI).

1. Tumor: 15-17 (5 micron scrolls), or 15-17 (5 micron unstained slides); 70% tumor  
(Any extra tissue would be saved and returned to the ECOG-ACRIN Central Biorepository and Pathology Facility.)  
[These will be used for the testing of (1) gene expression profiling, (2) Immunohistochemistry, (3) activating mutations by targeted sequencing in select patients with unknown mutational status, (4) methylation status of DNA sequences]
  2. PBMC/Serum: 5 vials PBMC and 3 vials serum  
(An extra vial requested would be saved at the IMCPL and used only for unexpectedly low recoveries and running assays on different days.)
  3. DNA (genomic): one yellow top tube  
(Remaining specimen would be saved at the IMCPL.)  
[This will be used for the testing of genomic variants potentially predictive of autoimmune colitis induced by ipilimumab]
- 

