## **3. Prediction of Autoimmune Colitis**

### **3.a. Targeted Deep Sequencing to identify genomic variants specific to patients who develop immune-related colitis after ipilimumab therapy.**

General: These assays will be conducted at the UPCI Cancer Biomarkers Facility (CBF) Genomics Core (Director: [name]).

We identified a genomic signature to predict colitis predisposition among patients undergoing neoadjuvant ipilimumab therapy for advanced melanoma (*Tarhini et al., Clustered genomic variants specific to patients who develop immune-related colitis after ipilimumab may predict this toxicity. Submitted to the 2014 ASCO Annual Meeting*). The proposed study will extend these findings in a larger patient cohort. Targeted, deep sequencing will focus on a customized 10 gene/9 SNP panel developed in our laboratory. PBMC (blood) samples ( $1 \times 10^6$  cells) will be extracted using the QIAamp DNA Micro kit (Qiagen, Valencia, CA) and DNA obtained by column purification will undergo QC to identify samples ( $>100$  ng/ul) with OD 260/280  $>1.8$  (Nanodrop ND-1000 spectrophotometer, NanoDrop, Wilmington, DE) and fragments  $\geq 300$  base pairs (Bioanalyzer 2100: 12000 DNA Chip, Agilent Technologies, Santa Clara, CA) for library

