construction. Primers for target genes will be used to generate amplicon libraries via PCR selection (Perkin Elmer 9700, Bridgeville, PA) (99°C x 2min, 15 cycles at 99°C x 15 sec, 60°C x 8 min, 10°C x hold) followed by enzymatic digestion and phosphorylation of the multiplexed amplicons. The amplicons are then indexed (Ion Xpress Barcode Adapters, Life Technologies, Grand Island, NY) and adapters ligated for attachment to Ion Spheres (ISP) in micro-reactors for clonal amplification using emulsion PCR (One Touch 2 instrument; 60 cycles, PGM 200bp kit v2). Templated ISPs are recovered and enriched using biotin labeled primers bound to streptavidin coated metallic beads (DynaBeads C1, Life Technologies). The ISPs are then washed, stripped from the streptavidin beads (125mM NaOH; 0.1% Tween 20) and sequencing is performed on the Ion Torrent Personal Genome Machine (PGM) using the 200bp sequencing kit v.2 and a washed, precalibrated semiconductor chip (318v.1 for 200bp libraries, Life Technologies) on the PGM platform. Sequencing comprising 500 flows (125 washes of each of 4 nucleotides) has provided 1000 x base depth of parsed barcoded reads aligned to Human Reference Genome HG19 on 10 samples undergoing simultaneous sequencing. BAM files (binary format), linked BAI files (indexed files) and variant call files (vcf) (Torrent Suite 4.0) are transferred from the Ion Torrent server (Dell Precision T7500, Intel Xeon Quad Core 2.93GHz, Ubuntu 10.04) to the analysis server (MacPro 5.1, Intel Xeon 6 Core 2.4GHz, OSX 10.8.4; GenomOncology Inc., Westlake, OH). A Galaxy Project plug-in (Pennsylvania State University, State College, PA) generates additional vcfs and INDELS using GATK (Genome Analysis Toolkit; UnifiedGenotyper v. 2.3), SAMtools (mpileup v. 0.1.18) and a manual variant caller algorithm (variant:  $\geq 5\%$  base calls differ from HG19 with  $\geq 300$  calls at Phred Score=20 or  $p < 0.01$ ). All variants and INDELS are validated by manual curation of the BAM file sequence using the Integrated Genomics Viewer (IGV Broad Institute). All patient samples will be compared for commonality of single nucleotide variants and INDELS based on colitis symptoms.

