### **Case Selection**

We plan to include all subjects accrued in E1609 ipilimumab study arms (A, D and C, F) and HDI study arm. Arms A and D treat patients with high dose ipilimumab (HIP), arms B and E with HDI and arms C and F with low dose ipilimumab (LIP).

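### The colitis-genotype test in Appendix XIX.9 states no analysis population and names neither arm nor dose, so read literally it pools HDI patients into a test of ipilimumab colitis; the loss is modest and validity is unaffected

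*Combined protocol and SAP*

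**What the plan says.** The analysis text for this secondary objective is two sentences in Appendix XIX.9. Each variant is tested "by logistic regression adjusting for potential clinical confounders including age and sex", with Benjamini-Hochberg control of the false-discovery rate at 5%. No analysis population, treatment arm or dose is mentioned.

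The population has to be taken from elsewhere in the appendix:

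- Case Selection (XIX.8), which covers every objective: "We plan to include all subjects accrued in E1609 ipilimumab study arms (A, D and C, F) and HDI study arm".
- Laboratory methods (XIX.6, item 3.a), on the "customized 10 gene/9 SNP panel": "All patient samples will be compared for commonality of single nucleotide variants and INDELS based on colitis symptoms".

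The purpose is stated more narrowly. Hypothesis 3 (XIX.1) is that "clustered genomic variants specific to patients who develop immune-related colitis after ipilimumab predict this toxicity". The specimen section (XIX.5) says of the genomic DNA: "This will be used for the testing of genomic variants potentially predictive of autoimmune colitis induced by ipilimumab".

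The appendix does name treatment in its other pooled models. The single-marker Cox model for RFS is adjusted for treatment arm, and the predictive-marker Cox model carries a treatment term coded HDI/HIP/LIP.

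**The concern.** The question is whether a germline variant predicts colitis in people given ipilimumab. A patient on HDI is not exposed on protocol, so that patient says nothing about this and enters either as a non-case whatever the genotype or as a case unrelated to it. Both dilute the odds ratio.

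Among ipilimumab patients, dose predicts severe GI toxicity. Leaving it out of a logistic model moves the estimate from a within-dose odds ratio to a marginal one closer to 1 and costs some precision. The model text asks for confounders. A randomized arm is not a confounder of germline genotype, so an analyst following the wording has no prompt to add it.

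At stake are the size of the reported odds ratio and some power in a correlative objective.

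**Working it through.** **Plan's own figure.** The appendix gives no sample size, power or odds ratio for this test, so there is nothing to reproduce. The yields can be taken from its predictive-modelling calculation, where (250 + 300) × 0.80 × 0.95 = 418, as stated.

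**Inputs from the documents**

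- Target arm sizes: 600 HDI, 500 HIP, 500 LIP (XIX.8). At 80% availability and 95% assay success: 500 × 0.80 × 0.95 = 380 per ipilimumab arm and 600 × 0.80 × 0.95 = 456 HDI. The same yield is assumed for DNA.
- Any-grade colitis: 8% at 3 mg/kg (Table 6) and 10.2% at 10 mg/kg (Section 1.5.4.1). These come from different studies with different attribution rules.
- Grade 3-4 GI irAEs: 2.8% at 3 mg/kg and 15.5% at 10 mg/kg (Table 3, CA184-022). Section 1.6 says of all organ classes together that "the CA184-022 trial suggested that the frequency of grade 3-4 irAEs was different between the 3 mg/kg and 10 mg/kg ipilimumab doses".

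**Assumptions.** Within-arm carrier odds ratio 2.0; 30% carriers; two-sided 0.05 per variant; HDI colitis rate 0%, 2% or 5%, unrelated to genotype. The documents give none of these.

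**Method.** In each ipilimumab arm, solve 0.7·p0 + 0.3·p1 = arm rate, with p1/(1 − p1) = 2·p0/(1 − p0). Fit the logistic model to the expected counts with and without the carrier term. The likelihood-ratio statistic is the non-centrality λ, and power = P(χ²₁(λ) > 3.84).

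**Expected events**

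| Outcome | 3 mg/kg: non-carriers (of 266) / carriers (of 114) | 10 mg/kg: non-carriers (of 266) / carriers (of 114) |
|---|---|---|
| Any-grade colitis | 16.83 / 13.57 | 21.62 / 17.14 |
| Grade 3-4 GI | 5.79 / 4.85 | 33.44 / 25.46 |

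HDI contributes 319.2 non-carriers and 136.8 carriers.

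**Pooled odds ratio by hand, any-grade colitis, no HDI events.** Carriers: 13.57 + 17.14 = 30.71 events among 114 + 114 + 136.8 = 364.8, so odds 30.71/334.09 = 0.0919. Non-carriers: 16.83 + 21.62 = 38.45 among 266 + 266 + 319.2 = 851.2, so odds 38.45/812.75 = 0.0473. Ratio 1.94.

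**Results: odds ratio, λ, power**

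| Analysis | Any-grade colitis | Grade 3-4 GI |
|---|---|---|
| Ipilimumab arms, dose in model | 2.00, 7.07, 75.8% | 2.00, 6.69, 73.5% |
| Ipilimumab arms, no dose term | 1.998, 7.06, 75.7% | 1.93, 6.34, 71.2% |
| All arms, no arm term, HDI 0% | 1.94, 6.78, 74.0% | 1.88, 6.09, 69.4% |
| All arms, no arm term, HDI 2% | 1.82, 6.08, 69.3% | 1.76, 5.46, 64.7% |
| All arms, no arm term, HDI 5% | 1.68, 5.28, 63.2% | 1.64, 4.75, 58.7% |

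The loss against the first row is 75.8 − 74.0 = 1.8 and 73.5 − 69.4 = 4.1 points with no HDI events, and 75.8 − 69.3 = 6.5 and 73.5 − 64.7 = 8.8 points at 2%. The dose term alone accounts for 0.1 and 2.3 points.

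**Range.** For grade 3-4 GI with no HDI events and 30% carriers, the loss is 2.3 points at odds ratio 1.5 (31.9% to 29.6%) and 0.9 at odds ratio 3 (98.6% to 97.7%). At 0.05/9 per variant and odds ratio 2.0, power falls from 42.6% to 38.0%.

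**Check by simulation** (4,000 trials per setting). Grade 3-4 GI with no HDI events gave powers of 72.2%, 70.0% and 67.7% for the first three rows. With no genotype effect, all three analyses rejected in 5.2% to 5.3% of trials.

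**The case against.** Four points can fairly be made against this.

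1. The covariate list is open, since age and sex are given as examples. A reader might infer that the plan excludes dose; it only fails to name it. This stands.
2. Case Selection serves the whole appendix, and other objectives need HDI. Every statement of the colitis test's purpose points to ipilimumab. A reader might infer that the plan instructs the analyst to put some 600 HDI patients into this model. The documents do not go that far; the defect is an unstated population. Even so, the only population wording available includes HDI, and nothing restricts this test.
3. A reader might take dose to be the established driver of colitis. The steep gradient is for grade 3-4 GI irAEs, with about 71 patients per dose. Any-grade colitis is 8% against 10.2% across studies, any-grade GI irAEs are 32.4% against 39.4%, and Section 1.5.4.7 describes overall irAE frequency as similar. For colitis without a grade limit, the dose term changes almost nothing.
4. HDI patients with no events act as extra genotype controls, so the test stays valid and loses little. This stands, but the irAE definition in Section 5.5.1.3 is not limited to ipilimumab, so some HDI patients could be coded as cases.

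Larger losses can be produced by taking any-grade GI irAEs as the outcome: at odds ratio 1.5, adding HDI patients with no events takes power from 69.8% to 60.9%. That is not the outcome XIX.9 names.

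**Conclusion.** The point holds as a gap in specification with a modest cost. The test does not state its population or name arm or dose, and its literal reading does not match its hypothesis. The odds ratio moves from 2.00 to 1.94 (any-grade colitis) or 1.88 (grade 3-4 GI) when HDI patients have no events, and to 1.82 or 1.76 when 2% of them are coded with colitis unrelated to genotype. These sizes rest on the assumed odds ratio, carrier frequency and HDI rate, and on which grade of colitis is analysed, which XIX.9 does not say.

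A reader might infer bias from confounding or a risk of false positives. Neither follows: dose is randomized and therefore independent of germline genotype, and the simulated type I error is nominal in all three analyses. This is a secondary objective of a banked-specimen study, and the trial's primary analyses are not touched.

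**What to change.** In XIX.9, state that the primary colitis-genotype test is run in patients who received at least one dose of ipilimumab (Arms A, C, D, F), with randomized dose arm (10 vs 3 mg/kg) as a covariate or stratum alongside age and sex. HDI patients may be kept for a separate descriptive check of whether a variant is specific to ipilimumab. Stating the colitis definition and grade in the same place would settle which row of the results applies.

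The cost is a sentence or two and one model term. Arm is known for every patient, and no new data or samples are needed. Restriction removes HDI from the primary test only; the descriptive check keeps the comparison that those genotypes can offer.

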#### **Detailed Analysis Plan for the Primary Objective**

**Association of individual markers with clinical outcome.** The association of each marker at each time point with the RFS will be assessed by Cox proportional hazard regression (CoxPH), adjusted for treatment arm and known prognostic factors such as age, sex, Breslow thickness, recurrent disease at study entry, ulceration of the primary tumor, lymph-node status, number of positive lymph nodes, completion of lymph node dissection prior to treatment, microscopic extranodal extension, and mitotic rate. Schematically, we will fit models of the following form:  $\lambda(t) = \lambda_0(t) \times \exp\{\beta_1 M + \beta_2 T + \beta_i \text{Covariates}\}$ , where M denotes marker value (e.g., the absolute lymphocyte count, ALC), T denotes treatment (HDI/HIP/LIP), the function  $\lambda(t)$  represents the relapse rate at time t, and  $\lambda_0(t)$  represents the corresponding baseline relapse rate. Because some long-term cures have been observed in patients with stages IIB – III melanoma treated with HDI and ipilimumab, we will also perform exploratory analyses using a cure-rate model for RFS as a supplement to the CoxPH regression analyses proposed above. The cure-rate model assumes that the population being studied is a mixture of two subpopulations: one of which is cured (proportion  $\pi$  of the study population), and the other of which is not (proportion  $1 - \pi$  of the study population). We represent the survival function in this latter subpopulation by  $S_2(t)$ . The survival function  $S(t)$  for the entire study population is a simple mixture of the two:  $S(t) = \pi + (1 - \pi)S_2(t)$ . Similar approaches will be used for the statistical analysis of OS data. To adjust for the multiple testing, the Benjamini and Hochberg’s (BH) method will be used to control the false-discovery rate (FDR) at 5%. ***Note that this marker-by-marker analysis is not intended for the feature selection of the multi-marker model building***

***described in the next section. This analysis is to test the marginal association of each candidate marker. The feature selection step for the model building is included in the cross-validation loop to avoid over-fitting.***

**Development and validation of the prediction model.** The model development will be carried out at two levels: within each Aim (i.e., using markers within the same category) and across Aims (using markers that are discovered in all Aims). The main goal is to develop a prognosis model of RFS in the HIP and LIP arms. However, we will also take the advantage of the availability of the HDI arm to develop a prognosis model for melanoma patients treated with HDI. Therefore, we will develop a prognosis model for each arm of the study. Given the uniqueness of this study population, we do not have a compatible independent validation cohort, *but our study population is large enough that we will randomly split the samples into two groups of equal size, using one of them as the **training set** and the other one as the **validation set**. However, to avoid over fitting, the validation set will be held out till the last stage of the study, where it will be used to validate the final models. The small model within each subgroup of the biomarkers will be evaluated through cross-validation within the training set.*

We will first use the Lasso Cox proportional hazard regression (LPHR) to develop a prognosis model for RFS using the training set. The Lasso was developed by Tibshirani 1996 and uses an  $l_1$  penalty to achieve a sparse solution, which allows simultaneous variable selection while fitting the model. This method has been applied to generalized linear regression and CoxPH models. Friedman et al. developed a fast algorithm for these methods and implemented it in a user-friendly R package, glmnet. Lasso has attracted more and more attention on the analysis of high-dimensional data because of its capability to perform the regression with outstanding accuracy in a large feature space, while simultaneously selecting the features. The tuning parameter will be trained through ten-fold (10x) cross validation within the training set. The linear combination score of the resulting model will be used to classify the patients into low-, intermediate-, and high-risk groups (cutoff at the 33% and 67% percentiles of the score). Hazard ratios (HRs) between the groups will be calculated. Log rank tests will be used to compare the RFS among these groups. The ability of this score to predict 1-year RFS will be evaluated using a time-dependent ROC curve. The area under the ROC curve (AUROC) will be calculated. An optimal cutoff point, which produces the best prediction (highest accuracy), will be chosen, and the corresponding sensitivity (SN), specificity (SP), and accuracy will be reported. The moderate number of candidate markers considered in each aim and the relatively large number of samples also enables us to use the regular CoxPH regression as a complement method to the LPHR. Markers will be evaluated for inclusion in the CoxPH model by forward stepwise selection. We will follow the same approach described above to evaluate the predictability of the model. Several popular machine-learning methods have been extended to handle right-censored data and predict subject survival status *at a specific time point*. We will use these methods as alternative methods to predict 1-year RFS for these patients and compare the performance of these methods to the LPHR model and Cox regression model. Specifically, univariate Cox regression will be used to evaluate the association of each individual marker and RFS. The BH method will be used to control the FDR at 5%. We will apply the random survival forest and the survival SVM to markers that passed the univariate analysis to generate a prognostic model to predict 1-year RFS. We will also use a bootstrap method in combination with the machine learning algorithm in marker selection. We will cross check the results of both methods for consistencies. The SN, SP, and accuracy will be calculated for each model and compared by McNemar tests between each pair of models. To avoid over fitting of the data, 10x cross validation within the training set will be used. In addition, ***the final models will be validated in the validation set.*** Specifically, the model parameters estimated using the training data will be applied to the validation set. For the survival model, the HR low-, intermediate-, and high-risk

groups (cutoff at the 33% and 67% percentiles of the score) will be calculated. The log rank test will be used to compare the RFS between the groups. The discrimination ability of the risk score on 1-year RFS will be assessed by time-dependent ROC analysis. *The same strategies will be used in the analysis of OS.*

